**NCT number: pending**

**Document date: December 17, 2020**

## STUDY PROTOCOL

After local ethics committee evaluation, patients over 65 years of age scheduled for elective cardiac surgery requiring extracorporeal circulation will be invited to participate. Those who are interested will be interviewed by a member of the research team who, in case of meeting the inclusion and exclusion criteria, will obtain the informed consent signature. After this, routine pre-anesthetic evaluation will be carried out plus preoperative cognition test (MiniCog), delirium screening (CAM) and assessment of frailty using the Clinical Frailty Scale (CFS).

Once in the intraoperative period, standard monitoring (EEG, NIBP, SatO2) will be established, plus installation of an arterial line with local anesthesia and a peripheral venous line for drug administration. A basal blood sample will be taken to study baseline inflammatory status (CRP). Subsequently, a SedLine® frontal electroencephalography (EEG) electrode (Root, Masimo) will be installed, and the patient will be asked to close his/her eyes to obtain a baseline recording for 5 minutes. Then, after pre-oxygenation (100% oxygen), the induction of general anesthesia will be initiated in a protocolized way: Fentanyl 5-10 ucg / Kg intravenous (i.v.), Propofol 0.5 mg / kg i.v. (plus rescue of 0.5 mg / kg i.v. after 1 minute if necessary), Vecuronium 0.1 mg / Kg i.v. and vasoactive drugs (ephedrine, phenylephrine or norepinephrine) to maintain mean arterial pressure (MAP) between ± 20% of baseline. Orotracheal intubation will be carried out on a regular basis and will be connected to standard mechanical ventilation (Tidal volume: 6-8 ml / Kg, Respiratory Rate: for exhaled CO2 between 32-35 mmHg, PEEP 5). The SedLine® monitor screen will remain hidden from the anesthesiologist in charge during baseline recording and induction (up to approximately 10 minutes after endotracheal intubation). After that, this phase of the study will end, and anesthesia and surgery will continue. Intraoperative variables such as duration of surgery and anesthesia, time in extracorporeal circulation, total drug use, temperature, among others, will be recorded. The anesthesiologist in charge can use the SedLine monitor to guide the administration of anesthetics once the initial phase (induction) has been completed according to usual practice. Upon completion of the case, the EEG data will be retrieved for further analysis.

At the end of the surgery, in post-cardiac anesthetic recovery unit (Cardiac PACU), POD evaluation will be performed using CAM / CAM-ICU twice a day (AM and PM) for the first 72 postoperative hours. In addition, a structured chart review will be carried out in order to identify records that describe POD. Patients will be considered to have POD if they present a positive evaluation with CAM / CAM-ICU or if the structured chart review is positive within the first 3 postoperative days.

## EEG ANALYSIS

We will record the EEG data using Sedtrace (SedLine®) electrodes on the forehead located approximately at Fp1, Fp2, F7 and F8, the ground electrode at approximately Fpz and the reference electrode approximately 1 centimeter above Fpz. The data will be recorded with a preamplifier bandwidth of 0.5 to 92 Hz, a sample rate of 89 Hz, with a resolution of 16 bits and 29 nanovolts. Electrode impedance will be kept less than 5 kΩ on each channel.

For each patient, we will select 2-minute EEG segments that will represent the baseline period, the response to the propofol bolus (burst suppression, yes or no) and the phase of maintenance of general anesthesia prior to cardiopulmonary bypass. We will visually inspect the selected segments in both time and spectral domains to ensure data quality. We will calculate the multitaper spectral estimates using Matlab's Chronux toolbox with the following parameters: window length  $T = 2$  seconds without overlap, product of time bandwidth  $TW = 3$ , number of tapers  $K = 5$ . We will equally weight the signals from Fp1, Fp2, F7 and F8 channels. Patients will be considered to present burst suppression if they present alternating episodes of spontaneous high amplitude electrical activity (bursts) followed by suppression periods longer than 1 second (electrical variability  $<10 \mu\text{V}$ ). These analyzes will be performed in time domain as well as spectral domain.

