## STATISTICAL ANALYSIS

Initially, we will study the association between burst suppression (yes or no) with POD (yes or no) using univariate logistic regression. In addition, we will perform a univariate analysis for known risk factors for PDO (preoperative cognition, frailty, temperature in CPB, etc). Subsequently, we will perform a multivariate analysis with logistic regression to study the association between burst suppression with POD, after confounding variables adjustment. We will then use our data to generate a ROC curve and determine the area under the curve, sensitivity, specificity, positive predictive value, and negative predictive value of burst suppression to predict POD. Finally, we will use our variables to create a predictive model of POD that includes the burst suppression and other known risk factors for POD.

For descriptive statistics, continuous data will be presented using the mean  $\pm$  standard deviation or the median and its interquartile range, as appropriate. In addition, the groups will be compared by Student's t test for independent samples or the Mann-Whitney U test according to their distribution. In the case of categorical data, they will be presented as absolute counts and their corresponding percentage. Differences will be studied using Fisher's test or Chi square. For the association study, univariate and multivariate linear or logistic regressions will be performed, as appropriate. A significance level of 0.05 with its respective 95% confidence interval will be considered. All calculations will be performed in R statistical language.

Sample size calculation: With a sample of 72 subjects, we will have 80% power to detect a difference if the proportion of patients that present POD and burst suppression is 0.66 and the proportion patients that present POD and that do not present burst suppression is 0.33 with a significance level of 0.05 using a chi-square test. Considering 10% data loss, we will recruit a total of 80 patients.

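### Does the burst-suppression label need a named amplitude statistic and channel rule before it can be used?

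*Combined protocol and SAP*

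**What the plan says.** The EEG Analysis section starts with segment selection: "For each patient, we will select 2-minute EEG segments that will represent the baseline period", the response to the propofol bolus (where the yes/no label is read) and maintenance before bypass. Quality control comes next: "We will visually inspect the selected segments in both time and spectral domains to ensure data quality". The multitaper settings follow, and directly after them: "We will equally weight the signals from Fp1, Fp2, F7 and F8 channels".

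The label is then defined. High-amplitude bursts must alternate with suppressions, "followed by suppression periods longer than 1 second (electrical variability" under 10 µV). The paragraph closes: "These analyzes will be performed in time domain as well as spectral domain". All four channels share one reference: "the reference electrode approximately 1 centimeter above Fpz".

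The Statistical Analysis section uses the label as the exposure in univariate and multivariable logistic regression. It will also "determine the area under the curve, sensitivity, specificity, positive predictive value, and negative predictive value of burst suppression to predict POD", and the label enters the prediction model. The sample size rests on it too: "we will have 80% power to detect a difference if the proportion of patients that present POD and burst suppression is 0.66", against 0.33 without burst suppression, with 72 subjects.

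**The concern.** Two details are missing from the text. Electrical variability is not tied to a statistic: it could mean peak-to-peak range, excursion from zero, or a standard deviation. The section also does not say whether the 10 µV limit must hold in one channel, any channel, all four, or their mean. The equal-weighting sentence stands just before the rule and the sentence on time and spectral domains just after it, so a reader could think the limit applies to an averaged trace. Averaging lets activity that differs between channels partly cancel, and F7 and F8 lie farther from the shared reference than Fp1 and Fp2.

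The stakes would be real. In a sample of 72, a few labels can move a p-value across 0.05. If an analyst could try two readings and keep the better one, the type I error would rise. Another centre also could not reproduce the sensitivity and predictive values without knowing how the test was read.

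**Working it through.** **The plan's own figure.** Inputs from the Statistical Analysis section: 0.66 against 0.33, alpha 0.05, 80% power, chi-square. Two-sided testing and equal groups are assumed. With pooled variance and no continuity correction, the mean rate is (0.66 + 0.33)/2 = 0.495 and

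n per group = [1.96·√(2·0.495·0.505) + 0.842·√(0.66·0.34 + 0.33·0.67)]² / 0.33² = 34.8, so 35 per group, 70 in all.

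Power at 36 + 36 is 81.3%, and 72/0.90 = 80. The stated 72 and 80 reproduce, and neither depends on the wording of the label.

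**Worst-case relabelling.** Take 24/36 against 12/36 with delirium (0.667 and 0.333). The uncorrected chi-square is 8.00, p = 0.0047. Move k patients, all with delirium, from burst suppression to none:

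| k | Split | p |
|---|---|---|
| 1 | 23/35 v 13/37 | 0.0095 |
| 2 | 22/34 v 14/38 | 0.018 |
| 3 | 21/33 v 15/39 | 0.033 |
| 4 | 20/32 v 16/40 | 0.058 |

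At k = 4 sensitivity falls from 24/36 = 0.667 to 20/36 = 0.556. The area under the curve, (sensitivity + specificity)/2, falls from 0.667 to (0.556 + 0.667)/2 = 0.611.

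**How likely the worst case is.** If four of the 36 burst-suppression patients are moved at random, the chance that all four have delirium is C(24,4)/C(36,4) = 10,626/58,905 = 0.18. With three or fewer, p is at most 0.018 (21/32 v 15/40).

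**Relabelling unrelated to delirium.**
- In both directions at rate f, the phi coefficient becomes 0.333·(1 − 2f). It must exceed 1.96/√72 = 0.231, so f is about 0.154, or 11 of 72.
- A yes under peak-to-peak in all channels is also a yes on the mean, so those two readings differ one way only. One-way moves in expected proportions give p = 0.046 at 12 patients and 0.053 at 13.

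**How far apart the readings are.** For a sine wave of amplitude A, a 10 µV limit means A < 5 µV (peak-to-peak), A < 10 µV (excursion from zero) or A < 10√2 = 14.1 µV (standard deviation). In simulated noise the excursion reading admits residual activity 1.7 to 1.8 times larger than peak-to-peak. For the mean of four equal channels with correlation r, a 10 µV channel limit becomes 10/√((1 + 3r)/4): 12.6 µV at r = 0.5 and 10.8 µV at r = 0.8.

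**Whether patients fall in the gap.** On simulated traces with equal channels and at least two suppressions required, all readings compared (peak-to-peak on all channels or on the mean, and ±10 µV on all channels) say yes when the residual SD is 2 µV or less. At 3 µV, peak-to-peak in all channels says yes in 0–1% and peak-to-peak on the mean in 96–100%. If F7/F8 residuals are assumed 1.5 times those at Fp1/Fp2, the two already part at 2 µV (0–4% against 100%). Every trace input is an assumption. The documents give no residual level, so the number of patients affected is unknown and may be zero.

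**Choosing between two readings.** If two labels differ at random in 4, 7 or 11 of 72 patients and the smaller p-value is kept, simulated type I error is 6.5%, 7.2% or 7.7%, against 4.5% for one fixed reading. This requires trying both and reporting the better.

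**The case for a change.** The best case for a change is that the label carries every main result, the omission is certain, and naming a reading costs a few sentences. That much stands: the text names neither the statistic nor the channel rule. The start of the two-minute window (a second propofol bolus is allowed after one minute) and the amplitude that makes a burst are also unstated.

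The rest is weaker. The equal-weighting sentence follows the multitaper settings and most naturally means pooling of spectra; the section never says that an averaged waveform is thresholded. A ±10 µV band allows a 20 µV swing, which strains variability below 10 µV. The largest contrasts therefore depend on unlikely readings. The label is also not the only input to sensitivity and predictive values, since delirium status is the other.

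Fixing one strict rule, such as all four channels at once with at least two suppressions, would be a preference and could have a cost. A stricter label could lower the share of patients labelled yes, and power at 72 is 75% if that share is 0.3, against 81% at 0.5. It would still leave the window start and the burst threshold open. Nothing in the documents shows labels being read with delirium known.

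**Conclusion.** No change to the plan follows. This is a gap in operational detail that EEG readers can fill sensibly. The plan states the phase of the record, the minimum suppression time and the voltage limit, and no stated rule is shown to give a wrong result. The size is conditional. Four patients out of 72 could cost significance only if all four are delirium cases moved the same way; if the relabelling is unrelated to delirium, 11 to 13 are needed. These figures assume equal groups and an observed result at the planning rates. The trace comparisons rest wholly on assumed signals. No reading is shown to be more accurate than another, and the documents do not show that any label or conclusion would change. The statistic, channel rule, window start and burst criterion can be written into the EEG readers' working instructions before labels are linked to delirium and reported with the results. The protocol text can stand.

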## STATISTICAL ANALYSIS

Initially, we will study the association between burst suppression (yes or no) with POD (yes or no) using univariate logistic regression. In addition, we will perform a univariate analysis for known risk factors for PDO (preoperative cognition, frailty, temperature in CPB, etc). Subsequently, we will perform a multivariate analysis with logistic regression to study the association between burst suppression with POD, after confounding variables adjustment. We will then use our data to generate a ROC curve and determine the area under the curve, sensitivity, specificity, positive predictive value, and negative predictive value of burst suppression to predict POD. Finally, we will use our variables to create a predictive model of POD that includes the burst suppression and other known risk factors for POD.

For descriptive statistics, continuous data will be presented using the mean  $\pm$  standard deviation or the median and its interquartile range, as appropriate. In addition, the groups will be compared by Student's t test for independent samples or the Mann-Whitney U test according to their distribution. In the case of categorical data, they will be presented as absolute counts and their corresponding percentage. Differences will be studied using Fisher's test or Chi square. For the association study, univariate and multivariate linear or logistic regressions will be performed, as appropriate. A significance level of 0.05 with its respective 95% confidence interval will be considered. All calculations will be performed in R statistical language.

Sample size calculation: With a sample of 72 subjects, we will have 80% power to detect a difference if the proportion of patients that present POD and burst suppression is 0.66 and the proportion patients that present POD and that do not present burst suppression is 0.33 with a significance level of 0.05 using a chi-square test. Considering 10% data loss, we will recruit a total of 80 patients.

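### With 72 patients and an open confounder list, ordinary logistic regression tends to overstate a true adjusted association; fix a short list and use Firth estimation

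*Combined protocol and SAP*

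**What the plan says.** The STATISTICAL ANALYSIS section begins with "the association between burst suppression (yes or no) with POD (yes or no) using univariate logistic regression". It then examines known risk factors one at a time, giving cognition before surgery, frailty and bypass temperature as examples and leaving the list open. The adjusted step follows: "Subsequently, we will perform a multivariate analysis with logistic regression to study the association between burst suppression with POD, after confounding variables adjustment". No penalised or bias-reduced estimator is named, so I read this as ordinary maximum likelihood (ML). The number of model terms is not stated.

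The size of the study is set in the same section: "With a sample of 72 subjects, we will have 80% power to detect a difference". The first of the two assumed rates is worded as "the proportion of patients that present POD and burst suppression is 0.66"; its counterpart for patients without burst suppression is 0.33. The calculation uses a chi-square test at the 0.05 level. The allowance for loss reads: "Considering 10% data loss, we will recruit a total of 80 patients". Neither the expected share of patients with burst suppression nor the number of POD events is given. The outcome is defined under STUDY PROTOCOL: "Patients will be considered to have POD if they present a positive evaluation with CAM / CAM-ICU". A positive chart review also counts.

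The section also plans a predictive model of POD from the same data.

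**The concern.** In small samples the ML log odds ratio from logistic regression lies, on average, further from zero than the true value. The gap widens as covariates are added. Here the sample is small and the number of covariates is uncapped.

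The adjusted odds ratio is the only planned effect estimate that controls for confounding. If burst suppression really is associated with POD, the study would tend to report that link as stronger than it is. This point is about that estimate, not about the discrimination or calibration of the later predictive model.

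**Working it through.** **Step 1. Reproduce the sample size.** I read 0.66 and 0.33 as POD risks with and without burst suppression. The plan's wording could also describe joint proportions, but the conditional reading reproduces its figure.

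- Effect size at a 1:1 split: w = 0.33 × 0.5 / √(0.495 × 0.505) = 0.330.
- N = (1.960 + 0.842)² / 0.330² = 72.07, two-sided. This matches the stated 72.
- The two-proportion formula without continuity correction gives 70, and 36 per group gives power 0.813.
- 72 / (1 − 0.10) = 80, as stated.

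**Step 2. Planning effect and events.**

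- OR = (0.66/0.34) / (0.33/0.67) = 3.94; log OR = 1.371.
- Events = 72 × [s × 0.66 + (1 − s) × 0.33], where s is the share with burst suppression. The result is 35.6 at s = 0.5, 28.5 at s = 0.2 and 42.8 at s = 0.8. Exposure is observed, not allocated, so s is an assumption.

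**Step 3. Simulate the adjusted analysis.** The setting was n = 72, s = 0.5 and about 49% POD, with 4,000 runs per scenario. The model was logit P(POD) = a + 1.371 × BS + 0.3 × ΣZ, with independent standard normal covariates Z whose sum correlates 0.3 with the latent exposure. The covariate effects and the correlation are assumptions. Each data set was fitted by ML and by Firth, which maximises log L + ½ log|I|, where I is the information matrix. Bias = (mean log OR − 1.371) / 1.371.

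| Covariates | ML mean log OR (bias) | OR from ML mean | Firth mean log OR | RMSE, ML vs Firth | ML Wald coverage |
|---|---|---|---|---|---|
| 0 | 1.414 (+3%) | 4.1 | 1.370 | 0.527 vs 0.508 | 0.954 |
| 3 | 1.485 (+8%) | 4.4 | 1.370 | 0.605 vs 0.539 | 0.951 |
| 5 | 1.564 (+14%) | 4.8 | 1.386 | 0.703 vs 0.579 | 0.941 |
| 8 | 1.676 (+22%) | 5.3 | 1.387 | 0.855 vs 0.618 | 0.929 |

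Bias is measured against the true conditional value. It is therefore not the legitimate difference between adjusted and unadjusted odds ratios. Non-converged ML runs (0 to 9 of 4,000) were dropped, which slightly favours ML.

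**Step 4. Vary the assumptions.** With covariates independent of exposure, true OR 4 and linear-predictor SD 1, the bias was 11%, 14% and 24% for 3, 5 and 8 covariates. A further run at OR 4 gave about 10%, 10% and 23%, with Firth within 3%. The ranges across runs are thus 8-11%, 10-14% and 22-24%.

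**Step 5. Null case and tests** (Step 3 design).

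| Covariates | Type I error, ML vs Firth | Rejection at OR 3.94, ML vs Firth | Difference |
|---|---|---|---|
| 3 | 0.053 vs 0.045 | 0.768 vs 0.750 | 1.8 points |
| 5 | 0.062 vs 0.050 | 0.749 vs 0.719 | 3.0 points |
| 8 | 0.070 vs 0.047 | 0.721 vs 0.672 | 4.9 points |

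These are likelihood-ratio tests, penalised for Firth. Under the null the mean ML log OR was between −0.018 and −0.004, so there is no bias to correct. Part of Firth's lower rejection rate comes from correcting the ML test's size.

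**Step 6. Effect on predicted risk.** With 5 covariates, mean Firth risk against observed was 0.497 vs 0.497 at about 50% POD, 0.401 vs 0.395 at 40% and 0.264 vs 0.248 at 25%. Firth pulls the average risk towards 0.5 when POD is not near 50%.

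**The case against.** The strongest objection is that the bias is modest unless the model is long. Only three risk factors are named. At three covariates the excess is 1.485 − 1.371 = 0.114 on the log scale, against an estimator SD of 0.594, or 0.19 SD. Wald coverage there is close to 0.95, so the planned 95% interval would be wide but honest. A short fixed list would control most of the problem with the ordinary estimator. All of this stands, and it is why the fix starts with the list. It does not dispose of the point, because the plan neither stops at three terms nor says where it stops. Even at three, Firth lowers RMSE from 0.605 to 0.539.

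A reader might infer several stronger claims that the documents do not support:

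- **That the reported odds ratio will be too large whatever the truth.** The excess exists only if there is a true association. The value near 4 is a planning assumption.
- **That the plan commits to a bias above 20%.** Those figures need about 8 terms, which the plan does not state.
- **That there will be 36 POD cases.** The plan gives no event count, and 36 needs a 1:1 split.
- **That Firth removes the bias at no cost.** It removes most of it on the log-odds scale. The arithmetic mean of the Firth odds ratio was still 4.61 to 4.98 against 3.94 with 3 to 8 covariates. Confounding and data-driven selection are untouched, and the rejection rate falls somewhat.
- **That univariate p-values will select the confounders.** The plan runs univariate analyses first but does not say so.

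**Conclusion.** The point holds as a conditional one. If the true odds ratio is near 4, ordinary logistic regression in 72 patients overstates the adjusted log odds ratio on average by roughly 8-11% with 3 covariates, 10-14% with 5 and 22-24% with 8. Firth estimation stays within about 3% and has lower RMSE in every setting tried. Type I error of the ML likelihood-ratio test also drifts above the plan's 0.05 as terms are added.

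The percentages rest on simulated covariate effects, and the number of terms is mine, not the plan's. With a short list the interval is still trustworthy and the gain is moderate. This is an inexpensive improvement that should be made before analysis; it is not a flaw that invalidates the study.

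**What to change.** In the STATISTICAL ANALYSIS section:

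1. Name one short, fixed set of preoperative confounders, state how many parameters it uses, and enter all of them regardless of univariate p-values. Bypass temperature falls outside such a set because it arises after the induction response.
2. Estimate the adjusted burst-suppression odds ratio by Firth penalised logistic regression, with profile penalised-likelihood 95% interval and test. Firth Wald intervals are not a substitute: their coverage was 0.96 to 0.98 here.
3. Report the ordinary ML estimate alongside as a sensitivity analysis.
4. Do not carry the Firth fit into the predictive model without an intercept correction. Another shrinkage method with internal validation would also serve there.

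The change costs a few sentences of wording and one R package; no new data are needed. Rejections fall by about 2 to 5 percentage points with 3 to 8 covariates, partly because the ML test's size is corrected, and the reported odds ratio will usually be somewhat less favourable.

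### The closing prediction model for delirium, in about 72 patients, has an open predictor list and no internal validation or calibration check, so uncorrected performance would on average be too favourable

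*Combined protocol and SAP*

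**What the plan says.** All references are to the combined protocol and SAP.

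- **The model.** The last analysis step in STATISTICAL ANALYSIS is "Finally, we will use our variables to create a predictive model of POD that includes the burst suppression and other known risk factors". Nothing more is said about how it will be built.
- **Candidate predictors.** Earlier in the same section: "In addition, we will perform a univariate analysis for known risk factors for PDO (preoperative cognition, frailty, temperature in CPB, etc". The list is three examples and an open end, and it is given for the univariate step, not for the model. STUDY PROTOCOL adds: "Intraoperative variables such as duration of surgery and anesthesia, time in extracorporeal circulation, total drug use, temperature, among others, will be recorded". It does not call these variables model candidates.
- **Performance measures.** The ROC step will "determine the area under the curve, sensitivity, specificity, positive predictive value, and negative predictive value of burst suppression to predict POD". These measures belong to burst suppression alone; none is named for the multivariable model.
- **Sample size.** "With a sample of 72 subjects, we will have 80% power to detect a difference", and then "Considering 10% data loss, we will recruit a total of 80 patients". The calculation rests only on comparing two proportions.

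No section mentions resampling, split samples, penalised fitting, calibration or a second cohort.

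**The concern.** A prediction model fitted and judged on the same small sample fits some of that sample's noise. Its AUC then tends to look better than it would in new patients. Its predicted risks are spread too widely: high risks too high, low risks too low. The calibration slope measures this; 1 is ideal, and values below 1 mean risks that are too extreme.

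The size of both effects depends on the number of predictors relative to the data. Here the number of patients is small and the number of predictors is left open. The model is a stated product of the study, and individual predicted risks are what such a model is for. Without a planned correction, readers would have no way to tell how much of its reported performance would carry over to other patients.

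**Working it through.** **Step 1. The plan's own figure.** Inputs from STATISTICAL ANALYSIS: POD rates 0.66 and 0.33, power 80%, significance level 0.05, chi-square test. Two-sided testing and equal groups are assumed.

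n per group = [1.96 × √(2 × 0.495 × 0.505) + 0.8416 × √(0.66 × 0.34 + 0.33 × 0.67)]² / 0.33² = (1.386 + 0.562)² / 0.1089 ≈ 34.8, so 35 per group and 70 in all. With 36 per group the power is 0.813. The effect-size form of the chi-square test (w = 0.330, N = 72) gives 0.7996. The plan's 72 is therefore reproduced, and 72 / 0.90 = 80 recruited.

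**Step 2. Expected delirium cases.** Cases = 72 × [p × 0.66 + (1 − p) × 0.33], where p is the burst-suppression prevalence (not in the documents, so varied).

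| p | cases in 72 |
|---|---|
| 0.2 | 28.5 |
| 0.3 | 30.9 |
| 0.5 | 35.6 |
| 0.7 | 40.4 |

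With four predictors, p of 0.3-0.5 leaves 30.9 / 4 = 7.7 to 35.6 / 4 = 8.9 cases per predictor.

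**Step 3. Overfitting with burst suppression plus three factors.** Simulation with n = 72, marginal POD rates held at 0.66 and 0.33, standard normal covariates, unpenalised logistic fit, 1,500 data sets per row, and performance measured in 4,000 new patients. Covariate strengths, correlation and prevalence are assumptions.

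| Three added factors | p | AUC apparent | AUC new patients | Optimism | Median slope |
|---|---|---|---|---|---|
| OR 1.5 per SD | 0.2 | 0.757 | 0.702 | 0.055 | 0.70 |
| OR 1.5 per SD | 0.3 | 0.769 | 0.717 | 0.052 | 0.72 |
| OR 1.5 per SD | 0.5 | 0.776 | 0.727 | 0.049 | 0.74 |
| OR 1.5 per SD | 0.7 | 0.766 | 0.716 | 0.050 | 0.73 |
| OR 1.5, correlation 0.3 | 0.5 | 0.799 | 0.755 | 0.044 | 0.76 |
| OR 2 per SD | 0.5 | 0.832 | 0.796 | 0.036 | 0.79 |
| No information | 0.2 | 0.688 | 0.598 | 0.090 | 0.54 |
| No information | 0.3 | 0.708 | 0.629 | 0.079 | 0.61 |
| No information | 0.5 | 0.721 | 0.651 | 0.070 | 0.65 |
| No information | 0.7 | 0.707 | 0.628 | 0.079 | 0.60 |

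Optimism is thus about 0.04-0.09 and the median slope about 0.54-0.79.

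**Step 4. Analytic cross-check.** Expected shrinkage S solves S = 1 + k / [n × ln(1 − R²/S)], with k predictors and R² the Cox-Snell value. For n = 72, k = 4, POD rates 0.33-0.495 and an assumed Nagelkerke R² of 0.15-0.35, S is 0.68-0.85. This overlaps the simulated slopes. With k = 6 it falls to 0.59-0.79, which shows the cost of a longer list.

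**Step 5. Burst suppression alone.** At p = 0.5, sensitivity is 0.66 / (0.66 + 0.33) = 0.667 and specificity is 0.67 / (0.67 + 0.34) = 0.663, so the AUC is (0.667 + 0.663) / 2 = 0.665. Simulation gives 0.664 both apparent and in new patients. The planned ROC step carries no material optimism.

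**Step 6. Does a bootstrap correction work?** (400 data sets × 150 resamples.)

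| Three added factors | p | AUC apparent | Corrected | True |
|---|---|---|---|---|
| OR 1.5 | 0.5 | 0.773 | 0.728 | 0.727 |
| OR 1.5 | 0.2 | 0.754 | 0.703 | 0.699 |
| OR 2 | 0.5 | 0.832 | 0.798 | 0.795 |
| No information | 0.5 | 0.722 | 0.664 | 0.652 |

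On average the correction is close, with slight under-correction when the factors are uninformative. In single data sets it is much less exact: with OR 1.5 and p = 0.5, the corrected AUC misses the true value by 0.052 on average, against 0.058 uncorrected, and is further from the truth in about 32% of data sets.

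Shrinking the coefficients by the bootstrap slope moves the median slope from 0.75 to 0.95 in that scenario. Mean absolute error of the predicted risk falls only from 0.100 to 0.095, and it rises in about 35% of data sets.

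**The case against.** The strongest reply is that the plan is brief rather than wrong. It does not say the model will be fitted without penalisation, names no performance measure for it, and does not state that uncorrected figures will be reported. A reader might infer that the sponsor intends to publish apparent performance; the text does not say so. This stands, and the harm is conditional on ordinary fitting and uncorrected reporting. The omission itself is not in doubt.

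A reader might also infer that every recorded intraoperative variable will enter the model, or that the univariate step will select predictors. Neither is stated. Scenarios with seven to nine covariates (optimism about 0.10-0.16, slope 0.34-0.53) are therefore weakly anchored, and long lists of pure noise sit badly with predictors described as known risk factors. They show the direction of travel but should not set the severity. Even the four-predictor case is an inference, because the three factors are named for another step.

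Finally, the remedy has limits. The corrected AUC varies between data sets with an SD of about 0.06-0.07, more than the roughly 0.05 optimism seen with informative factors at OR 1.5. Imprecision is then the larger problem, and the correction does not cure it. This also stands. It is a reason for reporting uncertainty and for the exploratory label, not for leaving the average bias in place.

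**Conclusion.** The concern holds in conditional form and should be fixed. The omission is certain from the text; its size rests on assumed prevalence, predictor strength, correlation and distribution. Under ordinary fitting and uncorrected reporting, burst suppression plus the three example factors would on average overstate the AUC by about 0.04-0.09 and give a median calibration slope of about 0.54-0.79. The milder end applies if the factors are informative, the worse end if they are not. In every multivariable scenario examined the direction was the same.

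A reader might go further and conclude that the study's main result is compromised or that 72 patients is an error. The documents do not support that: the sample size reproduces for the comparison it was designed for, and neither that comparison nor the single-marker ROC analysis is touched.

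**What to change.** Add to STATISTICAL ANALYSIS, before any analysis:

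1. **A short, closed predictor list**, for example burst suppression plus the three factors already named there (cognition before surgery, frailty and bypass temperature).
2. **Corrected performance as the reported performance.** Give the bootstrap optimism-corrected AUC and calibration slope, from at least 500 resamples with every modelling step repeated in each, together with their uncertainty.
3. **An exploratory label** for the model, pending external validation.

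Shrinkage or penalised fitting is optional. It improves the median slope, but at this sample size it reduces risk error only slightly and can worsen it in about a third of data sets.

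The cost is a predictor list written in advance and a few lines of R on data already being collected, with no change to sample size or to the powered comparison. The downside is less favourable reported performance.
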